Patients with atrial fibrillation (AF) who suffer an acute myocardial infarction (MI) are at increased risk for stroke (2% during index hospitalization), and mortality (14% 30-day mortality and 22% 1-year mortality) compared to those without AF.¹ In the TRACE trial, post-MI patients with AF during hospitalization had an increased 5-year mortality compared to those without AF (56%, OR 1.5).² Furthermore, AF post-MI has been associated with 30-day (HR 14.6) and long-term stroke (HR 2.29, mean follow-up 2.7 years).³ Even transient AF in hospital has been associated with stroke at 1-year (10.2%, HR 5.1), thus representing a target for therapeutic intervention⁴ In this study, patients were discharged home with only single or dual antiplatelet therapy despite eligibility for anticoagulation (mean age 70 years, 53% hypertensive, 34% diabetic). Thus, after an MI, AF is an important prognostic factor for predicting future events, including stroke and death.

1.1 New-Onset AF Post-MI

The prevalence of new AF post-MI is variably reported, with previous trial data reporting new AF in 3-7% of patients after extended follow-up (2-4 years).^{2, 3} A community cohort using ECG records identified new AF in 3.7% 3-30 days post-MI, and in 12% after longterm follow-up (6.6 years). However, despite the prevalence of AF, the majority of these episodes are asymptomatic, as demonstrated in two recent studies using continuous monitoring via implantable cardiac monitors. The first study (CARISMA) enrolled post-MI patients with LV dysfunction (EF \leq 40%) but no history of AF. The investigators demonstrated the risk of developing new AF was highest in the first 2 months post-MI (16%), with the prevalence of new-onset AF increasing to 28% at approximately 2 years follow-up.⁵ The ARREST study enrolled 50 post-STEMI patients with LVEF ≥40% who received percutaneous revascularization (PCI) within 7 days following MI.⁶ Over a 2year follow-up, AF was newly detected in 58% of the study population, with a median time to first episode of 4.8 months. Importantly, in both these studies >90% of patients were unaware of their AF highlighting the importance of vigilant surveillance of cardiac rhythm. As such a substantial proportion of patients may have undiagnosed AF and remain at increased risk of stroke.^{5, 6}

1.2 Limitations of Current Studies

A major difference between the aforementioned CARISMA and ARREST studies has to do with the method of surveillance. The CARISMA study utilized a loop recorder with an older AF detection algorithm that was reliant on ventricular rate. Specifically, AF was only detected at high heart rates (\geq 125 bpm) or in the presence of severe bradycardia (\leq 30 bpm). As many post-MI patients receive rate-slowing medications it is possible that they may not develop AF within the detection zones, and thus the prevalence estimate in this study likely represents an underestimate.⁷ Using an improved detection algorithm (R-R interval assessment), the ARREST study identified a greater proportion of new onset AF in a potentially healthier population (LVEF \geq 40%). However, in order to document this prevalence, patients were required to undergo an invasive procedure. The routine implantation of implantable loop recorders (ILRs) post-MI remains prohibitive due to its high cost and semi-invasive nature. External loop recorders may fit the ideal niche for AF monitoring in post-MI patients. As relatively affordable devices, external loop recorders provide extended monitoring and is best suited for patients with arrhythmia recurrence within 3-4 weeks.⁸ Furthermore, in contrast to patient activated external monitors (event recorders), external loop recorders have diagnostic rhythms for intelligent analysis and identification of AF, thus making the an ideal method to detect AF in asymptomatic patients, These devices have been used in syncope work-up and evaluation of palpitations, and more recently in the prolonged monitoring of cryptogenic stroke with great success.⁹ A non-invasive but intensive monitoring strategy post-MI may effectively identify individuals who develop AF after discharge and are eligible for oral anticoagulation (OAC).

1.3 Targets for intervention

Dual antiplatelet therapy (DAPT), is routinely prescribed to patients after an acute coronary syndrome owing to its beneficial effects in the prevention of stent thrombosis, myocardial infarction, and death after acute coronary syndrome (ACS).¹⁰⁻¹⁴ Unfortunately in the AF population, DAPT is inferior to OAC in the prevention of thromboembolic complications associated with atrial fibrillation or flutter (AF/AFL).¹⁵⁻¹⁷ As such, the identification of AF in this population has the potential to significantly alter the clinical management of these patients, as well as potentially improve outcomes.

2. RATIONALE:

After an MI, patients discharged home in sinus rhythm may develop AF that is asymptomatic, undetected, and undertreated. Previous studies (CARISMA and ARREST) have demonstrate high rates of new-onset AF recorded on ILR, although the routine implantation of ILRs post-MI remains costly and invasive. The external loop recorder may effectively identify patients with new-onset AF through a validated diagnostic algorithm and targeted monitoring during a high-risk period (immediately after hospital discharge).

3. PROPOSED RESEARCH

3.1 Hypothesis

Using a non-invasive but intensive monitoring strategy (30-day external loop recorder), we hypothesize that AF will be detected more frequently compared to standard care. Furthermore, intensive monitoring will result in higher rates of oral anticoagulation prescription (secondary outcome) compared to standard care.

3.2 Objectives

1) **Primary Objective -** To determine the incidence of new-onset AF at 30-days post-MI using an intensive monitoring strategy.

2) Secondary Objectives

- a) To determine the impact of intensive monitoring on oral anticoagulation rates at 90-days and 1-year after monitoring.
- b) To identify the risk factors for developing new-onset AF (i.e. demographics, MI characteristics, GRACE score).

c) To determine the variables associated with initiating or withholding anticoagulation in new-onset AF (i.e. CHADS₂, CHA₂DS₂-VASc, HASBLED scores).

3.4 Inclusion Criteria

- 1) Age 18 years or older.
- Patients with ST-elevation myocardial infarction (STEMI) or Non-ST-elevation myocardial infarction (NSTEMI; Third Universal Definition of MI¹⁸) with or without PCI. All patients must have troponin elevation.
- 3) No history of AF during hospitalization, at discharge, or pre-existing AF documented on history (i.e. hospital records, previous hospitalization, ECG records).
- 4) No anticoagulation for AF or other indications (i.e. LV thrombus, heart valves, venous thromboembolism/deep venous thrombosis).
- 5) No concomitant disease expected to reduce expected lifespan to <2 yrs.

3.5 Exclusion Criteria

- 1) Patients receiving CABG surgery during this hospitalization or planned cardiac surgery within the next 3 months.
- 2) Patients with spontaneous coronary artery dissection (SCAD), non-atherosclerotic coronary disease (NACAD), and Takotsubo cardiomyopathy are excluded from this study.
- 3) Patients with contraindications to anticoagulation.
- 4) Patients with a chronic skin disorder on the upper torso, or an allergy to medical tape or glue.

3.6 Outcomes

- Primary Outcome: development of atrial fibrillation or flutter lasting ≥30 seconds (consensus definition^{19, 20}) detected using external loop recorder
- 2) Secondary Outcome: anticoagulation prescription, AF-related hospitalization, and a composite secondary outcome of all-cause hospitalization, re-infarction, stroke, and death at 90-days and 1-year after completion of monitoring

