3.7 Methods

Upon enrollment, patients will be randomized (2:1 distribution for intensive monitoring, stratified by STEMI vs. NSTEACS) to receive standard care or intensive monitoring. Intensive monitoring entails wearing a Spiderflash (LivaNova) 30-day external cardiac monitor at discharge. A 30-day external cardiac monitor represents the most feasible, high-quality, non-invasive monitoring strategy possible, while maximizing the duration of uninterrupted monitoring beginning at discharge. Demographics, clinical characteristics, and risk factors for stroke and bleeding (i.e. CHADS₂, HASBLED) will also be collected at enrollment.

The research team will perform all aspects of SpiderFlash data acquisition and interpretation. The research team has purchased the SpiderFlash devices and the programming/analysis software. After patients have completed the 30-day recording, the information will be downloaded directly off the device (via SD card). There is no

industry involvement and no data transfer to a server or out of country. There is no relationship between the SpiderFlash provider and UBC/VCH, and no connection between the research team and SpiderFlash provider. All funds are provided by a research award attained by the trainee (CC).

Spiderflash ECGs will be interpreted by the trainee (CC, cardiology resident) with oversight from the supervising physician (JA). The reports will be distributed to the primary cardiologist and family physician. The standard care strategy includes a 12-lead ECG performed prior to discharge and at follow-up with the primary cardiologist (typically 4-8 weeks post-MI).

Cardiac medication review will be performed by the trainee (CC) at 90-days and 1-year post-monitoring (to allow adequate time for anticoagulant initiation). A telephone follow-up (15 min) and chart review will confirm anticoagulation status, and reasons for initiating or withholding anticoagulation.

Both the intensive monitoring and control groups will receive telephone follow-up at 90days to assess prescription status. No additional care or clinic visits are scheduled for the control group. All additional data (including ECGs performed by primary cardiologist and confirmation of anticoagulation status) in the intervention and control group will be performed via electronic chart review of Cardiology EMR.

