3.8 Sample Size Calculations and Statistical Analysis

Previous retrospective and cohort data has identified new-onset AF in 7-14% of patients in-hospital or within 2 days after MI.^{4, 21} Between 3-30 days, new AF occurs in 3.7% when ascertained through an electronic ECG database, with the remainder of AF (12%) developing during long-term follow-up (6.6 years).²¹ Thus, at 30-days post-MI, we anticipate that the standard care strategy will detect similar rates of AF to this cohort study (3.7%).

Using an ILR, new-onset AF was detected in 16% at 2-months (approx. 8% at 1-month, CARISMA).⁵ However, in the CARISMA study, AF was only detected when HR \geq 125 bpm, effectively missing AF at slower rates (<125 bpm).⁵ Up to half of patients (49%) with AF post-MI have heart rates \leq 94 bpm.⁷ Thus, we anticipate that an intensive monitoring strategy (30-day external cardiac monitor) will detect higher rates of AF (16%) after 30-days (double ILR rate given the heart rate limitations).

With a 2:1 randomization to intensive monitoring and using a 5% significance level (α =0.05), **216 patients** (144 patients with intensive monitoring and 72 patients with standard care) are required to have a 80% power (1- β =0.80) of detecting an increase in new AF (primary outcome) from 3.7% (standard care) to 16% (intensive monitoring). Accounting for a 5% drop-out, the final sample size is **240 patients (120 patients per group)**.

Statistical analysis will be performed using an intention-to-treat analysis for patients randomized to the intensive monitoring or standard care strategy. Regression analysis

will be used to compare rates of AF at 30-days between both groups. Time-to-event analysis will be used to compare the time to development of AF in both groups.

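### The primary outcome can only occur in patients who wear the loop recorder, yet the analysis compares both arms and assumes 3.7% in controls; no rule defines a control event

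*Combined protocol and SAP*

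**What the plan says.** - **Outcome (3.6).** The primary outcome is AF or flutter lasting at least 30 seconds, "detected using external loop recorder".
- **Who has the recorder (3.7).** "Intensive monitoring entails wearing a Spiderflash (LivaNova) 30-day external cardiac monitor at discharge". Standard care is a 12-lead ECG before discharge and another "at follow-up with the primary cardiologist (typically 4-8 weeks post-MI"). Other data in both arms come from electronic chart review, "including ECGs performed by primary cardiologist and confirmation of anticoagulation status".
- **Objective (3.2).** The primary objective names one strategy only: "To determine the incidence of new-onset AF at 30-days post-MI using an intensive monitoring strategy".
- **Hypothesis (3.1).** This is comparative: "we hypothesize that AF will be detected more frequently compared to standard care".
- **Analysis (3.8).** New AF is called the primary outcome, with 3.7% expected in standard care and 16% under intensive monitoring. Regression compares 30-day rates in the two groups, and a time-to-event analysis compares time to AF in both. The control rate comes from a cohort in which "new AF occurs in 3.7% when ascertained through an electronic ECG database" between days 3 and 30.
- **Eligibility (3.4).** Patients must have "No history of AF during hospitalization, at discharge, or pre-existing AF documented on history".
- **Other sources of AF data.** Section 4.6 names an endpoint adjudication committee (the principal investigator and the trainee, by consensus) without criteria. The follow-up form in Appendix 2 has a patient-reported AF item.

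**The concern.** The trial asks how much more AF intensive monitoring finds than standard care finds. An outcome that requires the recorder cannot occur in a patient who has none. If 3.6 is followed, standard care gets no credit for AF it detects. The control rate is then zero by construction, and an ordinary logistic or Cox model has no finite odds ratio or hazard ratio.

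If 3.8 is followed instead, the control event rule has to come from outside the plan. The plan does not say which recordings count, how a 12-lead ECG meets a 30-second criterion, or whether a patient's report is enough. Allocation is open to patients (4.2), and the two people who adjudicate endpoints (4.6) are also the two who interpret the recorder ECGs (3.7). That rule should be fixed before any data are seen.

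**Working it through.** **1. Can a control patient have a primary event?**

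- Under 3.6 as worded, no, because controls have no recorder.
- Under the intent of 3.1 and 3.8, yes. But the pre-discharge ECG cannot supply an event, since AF at discharge makes the patient ineligible (3.4). The only other scheduled control ECG is at 4-8 weeks post-MI, about days 28 to 56, so mostly after a 30-day endpoint. The rest would be unscheduled ECGs found by chart review, for which no rule is given.

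**2. The plan's own sample size.** Inputs from 3.8: p_C = 0.037, p_M = 0.16, allocation k = 2, α = 0.05 (taken as two-sided), power 80%.

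n_C = [z_0.975·√((1+1/k)·p̄(1−p̄)) + z_0.80·√(p_C(1−p_C) + p_M(1−p_M)/k)]² / (p_M−p_C)², with p̄ = (p_C + k·p_M)/(1+k) = (0.037 + 0.32)/3 = 0.119.

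- First term: 1.960 × √(1.5 × 0.1048) = 0.777
- Second term: 0.842 × √(0.0356 + 0.0672) = 0.270
- n_C = (0.777 + 0.270)² / 0.123² ≈ 72.5, rounded up to 73; total 73 + 146 = 219

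This is close to the stated 216 (144 + 72), for which the formula gives 79.7% power. So 216 depends on a control rate of 3.7%, which the wording of 3.6 does not allow.

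**3. How much one control event matters.** The documents give two allocations: 144:72 in the calculation, and 120 per group as the final size. Both are shown. Expected control events at 3.7%: 0.037 × 72 = 2.7; 0.037 × 120 = 4.4.

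Smallest number of monitored detections giving two-sided Fisher p < 0.05:

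| Control events counted | Of 144 (72 controls) | Of 120 (120 controls) |
|---|---|---|
| 0 | 9 (p = 0.031) | 6 (p = 0.029) |
| 1 | 13 (p = 0.038) | 8 (p = 0.036) |
| 2 | 16 (p = 0.039) | 10 (p = 0.034) |
| 3 | 20 (p = 0.034) | 12 (p = 0.030) |
| 4 | – | 13 (p = 0.041) |

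**4. Probability of declaring the monitor better.** This is the sum, over all pairs of counts significant in favour of the monitor, of Bin(c; n_C, p_C) × Bin(m; n_M, p_M). Each cell gives 144:72 / 120:120. The recorder rates of 8% (the one-month implantable-recorder figure) and 16% are from 3.8. A recorder rate of 3.7% represents no difference between strategies. Control rates of 1%, 2% and 5% are assumptions to show the range.

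| Control rate counted | Recorder 3.7% | Recorder 8% | Recorder 16% |
|---|---|---|---|
| 0 (3.6 as worded) | 9% / 29% | 82% / 92% | >99% / >99% |
| 1% | 4% / 12% | 54% / 68% | 98% / 99% |
| 2% | 2% / 5% | 35% / 45% | 94% / 97% |
| 3.7% | 0.6% / 0.9% | 15% / 19% | 79% / 88% |
| 5% | – | – | 65% / 75% |

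**The case against.** The intent can be read from the rest of the plan. Section 3.8 states what standard care is expected to detect, and 3.7 collects cardiologist ECGs by chart review in both arms. On that view 3.6 is loosely worded, the zero control rate is nobody's intention, and the 9% / 29% figures and the warning about infinite ratios apply only to a literal reading. The 8% recorder rate is one that 3.8 itself regards as an undercount and doubles, and power there is low mainly because the effect is small. The control rates of 1% and 2% are not tied to particular candidate rules. Fisher's test is also not the planned regression. Finally, an incidence objective is narrower than a comparison but does not strictly contradict it, and the 30-second criterion is referred to a consensus definition that could not be consulted here.

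Most of this stands as a limit on size. The literal figures are a bound, the sweep shows sensitivity rather than the effect of a specific rule, and at the planned effect the result is fairly robust. It does not remove the conflict between 3.6 and 3.8. Chart review is a source of data, not an event rule. An AF finding at a six-week visit would be an ordinary case, and the available text does not say whether it counts.

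**Conclusion.** The concern holds and must be fixed before analysis. The outcome in 3.6 and the comparison in 3.8 cannot both be applied as written, and neither supplies a definition of a control event. The objective in 3.2 should be brought into line, though the direct conflict is between 3.6 and 3.8.

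The size depends on the recorder yield. At the planned 16%, power is 79% / 88% with a 3.7% control rate and higher if fewer control events count, so the rule is unlikely to decide the result. At 8%, power runs from 82% / 92% with no control events to 15% / 19% at 3.7%, and the rule could decide it. Under equal detection at 3.7%, the literal outcome favours the monitor in 9% / 29% of trials, against 0.6% / 0.9% when control AF counts in full.

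These figures assume complete 30-day data, independent binomial counts and a two-sided exact test at 0.05. This is a fault in the endpoint definition, not in the arithmetic behind 216.

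**What to change.** Revise 3.2, 3.6 and 3.8 to give one primary outcome for both arms:

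- **Event.** New AF or flutter documented by any ECG source: loop recorder, Holter, telemetry, or a clinical 12-lead ECG found at chart review. Require at least 30 seconds on a continuous recording, or AF/flutter throughout a 12-lead tracing. Patient-reported AF counts only if an ECG confirms it.
- **Window.** Thirty days from one stated origin in both arms, for example discharge, when the recorder starts. Section 3.2 now counts from the MI, so the choice must be explicit. State also that AF first seen after the window, including at a later follow-up ECG, is not a primary event.
- **Adjudication.** The committee in 4.6 applies these criteria identically in both arms. Chart review records the full AF date and source.
- **Objective.** Reword 3.2 as the comparison with standard care. Report the recorder-only yield descriptively for the intensive arm.
- **Minor.** Time the 90-day and 1-year outcomes from the same origin, since controls have no completion of monitoring.

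The cost is text edits, two data items at a chart review already planned, and adjudication of control ECGs showing AF. Counting control AF lowers power from above 99% under the literal wording to 79% / 88% at the planned rates, about what the plan states, so N can stay. The 3.7% remains untested: it describes ECGs from days 3 to 30, while the scheduled control ECG falls mostly later. At a control rate of 1-2%, power at 16% would be 94-98% / 97-99%; at 5%, 65% / 75%.

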APPENDIX 2. Follow-up Case Report Form.

Study Site	S [*]	tudy ID	
Date of Follow-up $(VGH = 1; SPH)$	= 2) W	Which period? 3-month	1-year
Alive at Follow-up YES N	NO, cause of death	n:	
	date of death	n: (YYYY-N	/IM)
Signature of Person Completing CRF		Date:	
ANTIPLATELET/ANTICOAGU	LANT PRESCR	IPTION	
Antiplatelet ASA	Clopidogrel	Ticagrelor	Prasugrel
Anticoagulant 🗌 YES, name		NO	
dose	:		
CLINICAL OUTCOMES (since en	nrollment or last	follow-up)	
Myocardial Infarction	YES	NO	
With PCI	YES	NO	
Date of Last MI/PCI:			
With CABG	YES	NO	
Date of CABG:			
	(YYYY-MM)		
Stroke/CVA	YES	NO	
If so, what type?	Ischemic	Hemorrhagic T	IA Other
Date of Stroke/CVA:	(1 / 1 / 1 / 1 / 1 / 1 / 1 / 1 / 1 / 1 /		
Atrial Fibrillation (patient reported)	(YYYY-MM) $\Box VFS$		
Symptomatic?	TES TYES		
If symptomatic, number of ep	isodes:		
Date of cardiac arrest:	YES	NO	
	(YYYY-MM)		
Re-hospitalization (since discharge	YES	NO	
or last-follow-up) Reason for re-bospitalization	Stroko		1140
Reason for re-nospitalization	Other:		luic
Date of re-hospitalization:			
	(VVVV MM)		

Emergency Room Visits (without hosp	vitalization, sinc	ce discharge or last follow-up)
Reason for ER Visit	Cardiac (i.e.	chest pain, shortness of breath, palpitations)
INVESTIGATIONS (since dischar; ECHOCARDIOGRAM Echo since discharge/last follow-up? Date of Last Echo	ge or last follo YES (YYYY-M	)w-up) NO IM)
LV ejection fraction: Change in LV function:	Increase	% Decrease
PATIENT SATISFACTION (Complete at 3 month follow-up if p Did the patient complete full duration of If not, how many days?	of monitoring (ed the intensive monitoring strategy) (30 days)?
Please rate the comfort of wearing the Rating (1 to 10) If not comfortable why not?	SpiderFlash dev	evice (score from 1-10, 10 is very comfortable)
Did the patient have any difficulty using What difficulties?	g the device?	NO
Does the patient prefer intensive monit Prefers intensive monit Why or why not?	toring over no n onitoring	monitoring?
Did the patient feel satisfied with the car Please rate your satisfaction (score from Rating (1 to 10) If not satisfied, why not?	are they receive n 1-10, 10 is ver	ed as part of the study? ery satisfied).

*Please contact [name] (email: [contact], [contact], [contact]) or [name] ([contact]) with questions surrounding enrollment or eligibility.

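### Secondary outcomes are timed from the end of monitoring, which only the intensive arm has, so the control arm has no defined time origin and the two windows may differ

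*Combined protocol and SAP*

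**What the plan says.** Section 3.6 lists anticoagulant prescription, hospitalization related to AF, and a composite of clinical events, and places them "at 90-days and 1-year after completion of monitoring". The first secondary objective in section 3.2 uses the same clock: "To determine the impact of intensive monitoring on oral anticoagulation rates at 90-days and 1-year after monitoring". Section 3.7 schedules the medication review "at 90-days and 1-year post-monitoring (to allow adequate time for anticoagulant initiation").

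The monitoring itself belongs to one arm. Section 3.7 states: "Intensive monitoring entails wearing a Spiderflash (LivaNova) 30-day external cardiac monitor at discharge". For the other arm it states: "The standard care strategy includes a 12-lead ECG performed prior to discharge and at follow-up with the primary cardiologist". Nothing in the protocol gives controls a nominal end of monitoring.

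Section 3.7 also says: "Both the intensive monitoring and control groups will receive telephone follow-up at 90days to assess prescription status". It does not say from when the 90 days run.

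The follow-up case report form (Appendix 2) is one form for both arms, with a 3-month box and a 1-year box. It opens the event window at discharge, at enrollment or at the last follow-up, for example "Re-hospitalization (since discharge" or last follow-up. It also records how many days the device was worn if fewer than 30.

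**The concern.** A time origin that exists in only one randomised arm cannot define a between-arm comparison. Whoever schedules the control calls has to choose an origin, and the plan does not say which. If the choice is discharge, while monitored patients are counted from the end of their 30 days, the monitored arm is observed for longer. Because the form starts counting re-hospitalization at discharge, a later first visit lengthens that arm's cumulative window and does not merely shift it. Clinical events would then look more frequent in the monitored arm with no true effect.

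Taken literally, the rule also ties the assessment date in the monitored arm to something that happens after randomisation, namely when the patient stops wearing the device. That sits badly with the intention-to-treat comparison in section 3.8.

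Anticoagulation is affected differently. It is recorded as a yes or no status on the day of contact, so unequal timing means only that the arms may be compared at different elapsed times. It still matters, because a higher prescription rate is part of the hypothesis in section 3.1, and section 3.7 itself justifies the timing by the time needed to start treatment.

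**Working it through.** The plan states no figure for secondary follow-up, so there is none to reproduce. Its only power calculation concerns the primary outcome (section 3.8: 3.7% against 16%, 2:1, 216 patients). A two-sided 5% test without continuity correction gives 73 + 146 = 219, close to 216, so a two-sided 5% test is used below. The point does not depend on that calculation.

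**Step 1. Possible readings of the clock**

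| Reading | Monitored arm | Control arm | Windows |
|---|---|---|---|
| A. Both arms from discharge | day 90, day 365 | day 90, day 365 | equal, but contradicts 3.6 for the monitored arm |
| B. Controls given a nominal day 30 | day 120, day 395 | day 120, day 395 | equal for patients who wear the device for 30 days; not written anywhere |
| C. Monitored from day 30, controls from discharge | day 120, day 395 | day 90, day 365 | unequal |

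Under C, the exposure ratio is (30 + 90)/90 = 1.33 at the first assessment and (30 + 365)/365 = 1.08 at the second. If the clock follows actual wear, a patient who stops on day 15 (an illustration) is seen at day 105, and the ratio falls to 105/90 = 1.17.

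**Step 2. Apparent event rates under C with no true effect**

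Let p0 be the control risk at the control window T0, T1 the monitored window, and k the Weibull shape (k = 1 is constant hazard; k below 1 is risk concentrated early). The monitored risk is p1 = 1 − (1 − p0)^((T1/T0)^k). Both p0 and k are assumptions, since the documents give neither.

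With p0 = 20% at day 90:
- k = 1: 1 − 0.8^1.333 = 25.7%
- k = 0.7: 1 − 0.8^1.223 = 23.9%
- k = 0.5: 1 − 0.8^1.155 = 22.7%

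With p0 = 20% at day 365 and k = 1: 1 − 0.8^1.082 = 21.5%.

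**Step 3. False-positive rate**

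This is the rejection probability of the pooled two-proportion z-test, two-sided 5%, by full enumeration of both binomials. The group sizes are the two that section 3.8 prints. The plan names no test for these outcomes, so the test is also an assumption.

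| Assessment, hazard | Control | Monitored | 144:72 | 120:120 |
|---|---|---|---|---|
| Equal windows | 20% | 20% | 5% | 5% |
| 120 vs 90 days, constant | 20% | 25.7% | 14.8% | 18.6% |
| 120 vs 90 days, k = 0.7 | 20% | 23.9% | 9.3% | 11.3% |
| 120 vs 90 days, k = 0.5 | 20% | 22.7% | 7.0% | 8.2% |
| 395 vs 365 days, constant | 20% | 21.5% | 5.5% | 6.0% |

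With constant hazard at the first assessment, an assumed control risk of 10% gives about 9% (144:72) or 12% (120:120), and 40% gives about 25% or 30%. In the 20% constant-hazard case nearly all false rejections show more events in the monitored arm.

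**The case against.** The strongest reply is that unequal windows are not what the protocol prescribes. Section 3.7 names both arms in one sentence with one 90-day call, and reading C requires that single figure to carry two origins. The form is common to both arms with the same two visit boxes. Readings A and B give equal windows. This stands: a reader might infer that the plan sets day 120 against day 90, and the documents do not support that. They leave the control origin undefined.

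A reader might also infer that extra time lets anticoagulant starts build up in the monitored arm. The form does not collect it that way. It records current status without a start date, and stopping treatment can lower it, so the cumulative-risk arithmetic does not describe this outcome.

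No section says that the clock resets when the device comes off early. If it did, the gap would shrink, so early removal cannot be added to the 30 days as a further bias in the same direction.

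The false-positive rates rest on assumed event rates, an assumed hazard shape and a test that the plan does not name. Front-loaded risk after infarction is plausible and roughly halves the constant-hazard figures or more. The 1-year effect is negligible. The primary outcome is untouched, and section 4.4 calls this a pilot study.

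There is also a stated reason for counting from the end of monitoring: recordings are downloaded only after the 30 days, and prescribers need time to act. That supports a later assessment, but not a different one in each arm. None of these replies supplies the missing control origin.

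**Conclusion.** The point holds in a limited form. The stated timing rule cannot be applied to the control arm, and that conclusion needs no assumption. Whether the windows actually differ depends on a choice that the plan leaves open.

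If the arms are timed as in reading C, the monitored arm has up to 33% more exposure at the first assessment and 8% more at the second. For cumulative clinical events with no true effect and a 20% control risk at 90 days, a nominal 5% test would reject about 15% to 19% of the time under constant hazard, and about 7% to 11% with Weibull shape 0.5 to 0.7. With a 20% control risk at 1 year the figure is about 5.5% to 6%. Rates near 25% or above need an assumed 40% control risk at 90 days with constant hazard, and should not be taken as the expected size. For anticoagulation the conclusion is only that the arms may be assessed at different elapsed times. The plan should be changed, because the possible bias is avoidable at almost no cost.

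**What to change.** Define one time origin for both arms, either randomisation or discharge. Assess every secondary outcome on the same fixed study days in both arms, whatever the wear time. Day 120 and day 395 from discharge would serve as an example: they keep the interval after a 30-day recording that section 3.7 wants for anticoagulant initiation, and give controls the same interval. Count clinical events from that origin up to that day in both arms.

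Align the wording in sections 3.2, 3.6 and 3.7, and relabel the 3-month and 1-year boxes on the follow-up form with the chosen study days. Event dates on that form are printed to the month only, so cutting events at a common day would also need the day recorded or taken from the chart.

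The cost is a change of wording and of call dates, with no extra contacts. It is best made before follow-up calls begin, because prescription status on a common day may not be fully recoverable once the calls have been made on different days.
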